8.1.3 Assessment of Adverse Events by the Investigator

The Investigator will assess the severity (intensity) of each adverse event as mild, moderate, or severe, and will also categorize each adverse event as to its potential relationship to study drug using the categories of Yes or No, as defined below.

Assessment of Severity:

Mild – An event that is easily tolerated and generally not interfering with normal daily activities.

Moderate – An event that is sufficiently discomforting to interfere with normal daily activities.

Severe – An event that is incapacitating with inability to work or perform normal daily activities.

Causality Assessment:

The investigator's assessment of causality must be provided for all AEs. The causality is the determination of whether there exists a reasonable possibility that the study drug itself (eg, gemcabene or placebo) caused or contributed to an AE.

If the final determination of causality is unknown and the investigator does not know whether the study drug caused the event, then the event will be handled as "related to study drug" for reporting purposes. If the investigator's causality is "unknown, but not related to study drug", this should be clearly documented on study records.

The relationship of an adverse event to the administration of the study drug will be assessed according to the following definitions:

No (unlikely related, unrelated, not related, no relation) – The time course between the administration of study drug and the occurrence or worsening of the adverse event rules out a causal relationship and another cause (e.g., medical history, concomitant drugs, therapies, and complications) is suspected.

Yes (possibly related, related) – The time course between the administration of study drug and the occurrence or worsening of the adverse event is consistent with a causal relationship and no other cause (e.g., medical history, concomitant drugs, therapies, and complications) can be identified.

The definition implies a reasonable possibility of a causal relationship between the event and the study drug. This means that there are facts (evidence) or arguments to suggest a causal relationship.

The following factors should also be considered:

- The temporal sequence from study drug administration -
 - The event should occur after the study drug is given. The length of time from study drug exposure to event should be evaluated in the clinical context of the event.

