9.4 Handling of Missing Data

Missing values at baseline will not be imputed in any situation. For efficacy analyses, values missing post-randomization will be imputed using LOCF (unless otherwise specified); only post-randomization values on treatment will be used for imputation. For example, if a subject has Week 12 efficacy parameters measured more than 2 days after their last dose, their Week 12 efficacy values will be imputed using the last non-missing value while on treatment (eg, Week 8). The imputed values will be used in summaries and analysis. For safety analyses, observed case data will be used.

Imputation will not be conducted for AEs missing severity or relationship to study medication. AEs missing severity will be excluded from summaries of AEs by severity. Adverse events missing relationship will be excluded from summaries of related AEs.

Rules for partial and missing dates for prior and concomitant medications and smoking status are given in [Appendix 2](#).

Drug interruptions with partial start and/or stop dates will be assumed to be 1 day in length, and will be assumed to have occurred in the visit interval prior to when the interruption was collected (eg, if a drug interruption with partial dates was collected at the Week 8 visit, we will assume that the interruption occurred between the previous visit [eg, Week 4] and the Week 8 visit).

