If a subject has more than 1 TEAE at a given level (eg, SOC and PT), the subject will only be counted once within that level. When summarizing TEAEs by maximum severity or causality, at each level of summarization, subjects who report 1 or more TEAEs within that level are only counted once at that level using the event of greatest severity (in severity tables) or strongest relationship to study drug (in causality tables). All tables will show the number and percent of subjects with at least 1 TEAE (or SAE, per the criteria on the table). For example, the table of related SAEs will include a row for number and percent of subjects with at least one related SAE. Additionally, a drug-related TEAE is defined as a TEAE with an assigned relationship of “related.” A listing containing all AEs (pre-treatment and TEAEs) will be created; AEs that are not treatment-emergent will be flagged as non-treatment-emergent. Additionally, a listing containing AEs missing severity or relationship to the study drug will be provided; AEs that are not treatment-emergent will be flagged as non-treatment-emergent.

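### The SAP leaves adverse events with no recorded relationship out of the related-event tables, which sits poorly with the protocol's cautious default for undetermined causality

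*SAP*

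**What the plan says.** **SAP.** Section 9.4 sets the rule in two steps. First, "Imputation will not be conducted for AEs missing severity or relationship to study medication". Second, "Adverse events missing relationship will be excluded from summaries of related AEs". Section 12.1 works the same way from the other end: "a drug-related TEAE is defined as a TEAE with an assigned relationship of" related. Section 12.1 also provides a safeguard: "a listing containing AEs missing severity or relationship to the study drug will be provided".

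**Protocol.** Section 8.1.3 says that the investigator's "assessment of causality must be provided for all AEs", and that each event is classified "using the categories of Yes or No, as defined below". There is no third category. For the undecided case it sets a condition: "If the final determination of causality is unknown and the investigator does not know whether the study drug caused the event". Where that condition is met, the protocol takes the cautious side: "then the event will be handled as 'related to study drug' for reporting purposes". It then allows one exception: the investigator may hold that the cause is unknown but is not the study drug, provided that this is clearly documented.

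**The concern.** The protocol resolves doubt about causality towards related, and an investigator has to say so expressly to move an event out of that default. The SAP resolves an empty field by omission. If an undetermined event reaches the database as a blank, it falls under the SAP rule, although the protocol's principle would have it handled as related.

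The SAP also takes the opposite approach to another missing adverse event item. Under section 12.1, an event with no start date is taken to be treatment-emergent. No reason is given for handling a missing relationship differently.

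At stake are all the counts in SAP 12.1 that depend on relatedness: related treatment-emergent events, related serious events, discontinuations for related events, and deaths due to a related event. Protocol 9.3.2 plans no statistical analysis of safety, so these descriptive counts are what a reader will use. Safety within each statin stratum is a secondary objective, and there the groups are small. Compared with counting blanks as related, leaving them out can only keep the related counts the same or lower them.

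**Working it through.** The plan states no figure on this point, so the check compares the texts and then sizes the effect of one subject.

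**Step 1: can an undetermined event end up blank?** Protocol 8.1.3 gives two definitions. No requires timing that rules out a causal link, with another cause suspected. Yes requires compatible timing and no other identifiable cause. An event with compatible timing and a plausible alternative cause meets neither definition in full. With no box for undetermined, a blank is possible even though an assessment is mandatory.

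**Step 2: follow an undetermined event through both documents.** This assumes that the protocol's Yes is the SAP's assigned relationship of related.

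| How it reaches the database | Protocol 8.1.3 | SAP 9.4 and 12.1 | Agree? |
|---|---|---|---|
| Entered as Yes | Related | Counted as related | Yes |
| Entered as No, with the documented exception | Not related | Not counted as related | Yes |
| Left blank because the investigator could not decide | Handled as related for reporting | Left out of related summaries | No |
| Left blank by oversight, never resolved | No explicit rule | Left out of related summaries | Open |

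The documents part in the third row. In the fourth, the protocol has no explicit rule, but its cautious principle and the SAP's own start-date convention point towards counting the event.

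**Step 3: where a blank event still appears.** It stays in the SAP 12.1 tables of all treatment-emergent events and, if serious, of all serious events. It also appears in the listing of events with missing severity or relationship.

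**Step 4: size per affected subject.**

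Inputs: 52 randomized subjects per arm, and 26 per arm within each statin stratum (SAP 9.1). I assume that all are dosed and form the denominator. The number of affected subjects, k, is not given in the documents; 1 to 3 is an assumption for illustration.

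Formula: change in related-event rate = 100 × k / n.

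| k | Arm, n = 52 | Arm within stratum, n = 26 |
|---|---|---|
| 1 | 1.9 points | 3.8 points |
| 2 | 3.8 points | 7.7 points |
| 3 | 5.8 points | 11.5 points |

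A subject contributes to k only if the blank event is that subject's sole potentially related event. A subject with another event assessed as related is already counted in the rate of subjects with any related event. The same condition applies at each level of a table, such as a preferred term.

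**The case against.** The strongest reply is that the two rules concern different data states. The protocol speaks of a causality question that was considered and stayed undetermined; the SAP speaks of a field with no value. If sites follow the protocol and enter such an event as Yes, the SAP counts it. The overlap arises only when an undetermined event is left blank, which itself departs from the requirement to give an assessment. This stands. A reader might infer that the SAP does the opposite of the protocol; the documents do not support that.

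Second, the protocol's rule is limited to reporting. It sits in the section on investigator assessment, shortly before the sections on serious event and expedited reporting, and may not have been meant for summary tables. The protocol's analysis section, 9.3.2, calls for observed case data and has no rule for missing causality. So a reader might infer an undeclared protocol change because SAP section 8 does not list one, but that inference is weak.

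Third, a reader might infer that the SAP classifies blanks as not related. It does not: it plans no table of unrelated events, and the events remain in the all-event tables and the listing. Protocol 10.1.5 also sends missing data back to the site as queries, so few blanks should remain.

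Fourth, causality is assessed blind (protocol 5.3), and nothing suggests that blanks would differ by arm. The documents support no claim of a biased comparison between arms. No hypothesis test on safety is affected, and counting blanks as related can overstate relatedness.

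These points limit the size and wording of the concern. They do not remove it: the listing makes blanks visible but leaves the table counts unchanged, and the SAP gives no reason for choosing the less cautious default.

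**Conclusion.** The point holds as a minor one. SAP 9.4 departs in principle from the cautious handling of undetermined causality in protocol 8.1.3, and from the SAP's own treatment of missing start dates. It does not contradict the protocol word for word.

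The rule can only understate related-event counts relative to a count-as-related default. The size is 1.9 percentage points per affected subject in an arm and 3.8 points in an arm within a statin stratum, under the planned group sizes and only where the subject has no other related event. The number of affected subjects is unknown and may well be zero. The conclusion rests on one possibility that the documents leave open: that some undetermined events reach the locked database with the relationship field empty.

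**What to change.** Change the second sentence of the rule in SAP 9.4 and the definition of a drug-related event in SAP 12.1 so that they say the following:

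- An adverse event whose relationship is still missing or undetermined after queries is counted as related in all summaries of related treatment-emergent and related serious events.
- An event for which the investigator documented that the cause is unknown but is not the study drug is not counted as related, in line with protocol 8.1.3.
- Each affected table carries a footnote with the number of events assigned in this way, by treatment group.
- The listing of events with missing severity or relationship stays.

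The protocol has the exception documented in study records, so the query on a blank field should ask whether it applies; otherwise the programmer may not be able to identify it.

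The cost is a small edit in two SAP sections, a short derivation and a footnote, with no new data collection beyond the queries already planned. The downside is that related counts may rise slightly and could overstate relatedness. The footnote lets a reader see by how much.

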9.5 Interim Analysis

There is no planned interim analysis.

9.6 Visit Windows

Visit windows will be used to classify scheduled (except the Follow-up Visit), unscheduled, and early termination (ET) visits according to [Table 2](#). below to ensure that all visits have the potential to contribute to summaries. If 2 or more visits occur within the same analysis window, data from the visit closest to the target day will be used in summaries and/or analysis; if the visits are the same distance from the target day, data from the later date will be used. Data for laboratory parameters scheduled to be measured post-randomization at only the Week 12 or ET Visit (ie, HbA1c, C1 hsCRP, SAA, fibrinogen, adiponectin, FPG, and insulin) will be summarized under the Week 12 Visit. If there is more than one value, the latest will be used. For efficacy, parameters measured after last dose + 2 days will not be considered. Except for adverse events, for safety, parameters measured after last dose + 5 days will not be considered.

Table 2. Visit Windows for Assessments Done at Day 1, Weeks 2, 4, 8, and 12^a

Visit	Target Study Day	Visit Window
Day 1	1	(1)
Week 2	15	(2, 22)
Week 4	29	(23, 43)
Week 8	57	(44, 71)
Week 12	85	> 71

^a. As Apo and select urinalysis parameters are not measured at Week 2, the Visit Window for Week 4 for Apo and urinalysis parameters is (2, 43). Remaining urinalysis parameters are not measured at Week 2 or Week 8; thus, the Visit Windows for Week 4 and Week 12 are (2, 57) and > 57, respectively.

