6.6 Early Termination Visit and Withdrawal Procedures

Subjects must fast (at least 10 hours) prior to this visit.

For subjects who are withdrawn from the study prior to completion, the following procedures will be performed at the ET Visit:

- Perform full physical examination;
- Record vital signs and weight;
- Collect urine sample for urinalysis including urine protein:creatinine ratio, albumin:creatinine ratio and NGAL;
- Perform serum pregnancy test (for women of child-bearing potential only);
- Obtain blood sample for the following:
 - Safety chemistry panel, coagulation, and hematology;

- Fasting lipid panel, LDL-C ultracentrifugation (in subjects with TG \geq 400 mg/dL) and apolipoproteins;
- Fasting insulin and FPG
- CI
- HbA1c;
- hsCRP, SAA, adiponectin and fibrinogen; and
- Reserve samples;
- Perform 12-lead ECG;
- Assess and document study drug compliance; and
- Assess adverse events and update concomitant medications.

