8.1.4.2 Creatinine increase

If, at any visit, a creatinine increase >0.3 mg/dL (27 μ mol/L) from baseline or a GFR decrease of >15 mL/min from baseline is observed, a repeat chemistry will be performed. The subject's past medical history, concomitant medications (including over the counter drugs and herbal supplements), and any recent symptoms (e.g., fatigue, malaise, polyuria/oliguria, or palpitations) will be reviewed to determine a potential etiology and make a clinical assessment of the significance of the finding.

During the study, clinically significant abnormal results in NGAL will be used as a means of identifying subjects who have unremarkable creatinine/BUN values at the time of assessment but may require additional or closer/follow-up monitoring of renal studies.

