The following laboratory parameters will be summarized at baseline and at each post-baseline time point by treatment group. Additionally, CFBL to each time point (including end of treatment), if appropriate, for each of the following laboratory parameters will also be summarized by treatment group. If, for a given subject at a given visit, the absolute count of neutrophils are not provided but segmented and band neutrophils are, segmented and band neutrophils are summed to determine the absolute count of neutrophils. If only segmented neutrophils are provided, they are used as the absolute count of neutrophils. Similarly, if neutrophils/leukocytes are not provided at a given visit but neutrophils (segmented)/leukocytes are, neutrophils (segmented)/leukocytes are used as neutrophils/leukocytes. If a laboratory value is lower or higher than the detection limit, the value will not contribute to summary statistics but will be included in the listings.

- **Chemistry:** ALT, albumin, ALP, AST, bicarbonate, BUN, calcium, chloride, creatine kinase (CK), creatinine, gamma-glutamyl transferase (GGT), glucose, lactate dehydrogenase (LDH), phosphorus, potassium, sodium, (total) bilirubin, (total) protein, estimated glomerular filtration rate (GFR)
- **Coagulation:** prothrombin time, activated partial thromboplastin time, international normalized ratio
- **Hematology:** hemoglobin, hematocrit, leukocytes, basophils, eosinophils, lymphocytes, monocytes, neutrophils, platelets, red blood cell count, mean corpuscular hemoglobin concentration, mean corpuscular hemoglobin, mean corpuscular volume
- **Urinalysis:** pH, specific gravity, NGAL, creatinine, protein, protein/creatinine ratio, albumin, albumin/creatinine ratio

Out-of-range values will be assessed using shift tables. Laboratory values will be identified as low, normal, or high based on the normal ranges provided by the central laboratory. Shift tables for each parameter will display, for each treatment group, the number of subjects with low, normal, and high values at baseline and end of treatment. Additionally, a summary will be provided of the number of subjects who shifted to high or low during the study. The denominators will be the number of subjects at risk for shifting, ie, the subjects at risk for shifting to low are those with high or normal values at baseline, and the subjects at risk for shifting to high are those with low or normal values at baseline.

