Potentially clinically significant (PCS) tables will also be used to summarize out-of-range values for safety laboratory parameters. The PCS values are found in Table 3. The number and percent of subjects meeting the criteria below for single occurrences and consecutive (multiple) occurrences will be summarized by treatment group. The number and percent of subjects meeting the criteria below for single occurrences will be repeated for each statin-intensity stratum. Summaries will be given for any time post-baseline. The denominator for a given percentage will be the number of subjects who had a post-baseline assessment for the corresponding parameter. Additionally, for subjects with at least 1 post-baseline laboratory value meeting the PCS criteria, all laboratory values will be provided in a listing.

Table 3. Lab PCS Criteria

Laboratory Parameter	Unit	PCS Criteria
ALT	U/L	> 2 × ULN
AST	U/L	> 2 × ULN
BUN	mg/dL	> 2 × ULN
Creatine kinase	U/L	> 3 × ULN
Creatinine	mg/dL	> 0.3 increase from baseline
Estimated GFR	mL/min	Decrease > 15 from baseline
Hemoglobin	g/dL	Decrease > 1.5 from baseline
Urinalysis Parameter	Unit	PCS Criteria
Blood	-	present
Protein (qualitative)	-	present
Protein (quantitative)	-	> ULN
Protein/creatinine ratio	mg/mmol	> ULN

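### Does the last-dose-plus-5-days limit in SAP 9.6 leave the laboratory PCS and shift counts in SAP 12.2 undefined?

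*SAP*

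**What the plan says.** SAP 9.6 (Visit Windows) closes with a general limit: "Except for adverse events, for safety, parameters measured after last dose + 5 days will not be considered". SAP 9.2 uses the same 5 days to define end of treatment for safety parameters.

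SAP 12.2 first describes shift tables from baseline to end of treatment, then adds that "a summary will be provided of the number of subjects who shifted to high or low during the study". PCS values are counted "for single occurrences and consecutive (multiple) occurrences will be summarized by treatment group", and the counts "for single occurrences will be repeated for each statin-intensity stratum". On timing it says: "Summaries will be given for any time post-baseline". It also provides that "for subjects with at least 1 post-baseline laboratory value meeting the PCS criteria, all laboratory values will be provided in a listing". The opening of SAP 12 sends all safety data to listings.

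Some samples are planned after dosing ends. Protocol 8.6 and SAP 12.2 call for a creatinine recheck 2 weeks (±3 days) after last dose when the Week 12 or early termination (ET) result is abnormal to a clinically significant degree. Follow-up laboratory tests come at 4 weeks (±3 days), only in subjects with an abnormal Week 12/ET result or an ongoing treatment-related event. Protocol 8.1.4.2 says that if creatinine rises by more than 0.3 mg/dL "or a GFR decrease of >15 mL/min from baseline is observed, a repeat chemistry will be performed", and gives no deadline. Protocol 6.6 introduces the ET panel with "For subjects who are withdrawn from the study prior to completion, the following procedures will be performed at the ET Visit", and does not limit how long after last dose it may be drawn.

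**The concern.** The timing phrases in SAP 12.2 have no upper limit and do not refer back to SAP 9.6. Read alone, they would admit a creatinine value taken four weeks off drug; SAP 9.6 would not. If programmers could choose, the PCS and shift counts would depend on the choice.

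Renal effects are a named safety focus in SAP 6.3. Protocol 1.3 regards the creatinine rise seen earlier as benign partly because it resolved about 2 weeks after stopping. Under the SAP 9.6 limit, the samples that bear on this enter no laboratory summary table, and no visible table shows recovery. That looks like collecting the key data and then leaving them in listings.

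**Working it through.** **Inputs.** Limit: last dose + 5 days (SAP 9.6). Recheck: 14 ± 3 days; Follow-up: 28 ± 3 days (Protocol 8.6 and 6.5). Arm size: 52 overall and 26 per statin stratum (SAP 9.1). Week 12 target: Day 85; Week 8 window: Days 44 to 71 (SAP 9.6, Table 2).

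**Step 1. Do the two wordings select different data?** The recheck falls at 14 − 3 = 11 to 14 + 3 = 17 days after last dose. Follow-up falls at 28 − 3 = 25 to 28 + 3 = 31 days. The earliest are 11 − 5 = 6 and 25 − 5 = 20 days past the limit. With last dose on Day 85, the limit is Day 90, the recheck Days 96 to 102 and Follow-up Days 110 to 116. So yes: SAP 9.6 excludes every on-schedule off-drug sample, and a literal reading of 12.2 would admit them.

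**Step 2. Which tables could differ?** By-visit summaries and the baseline-to-end-of-treatment shift table could not; SAP 9.6 and 9.2 fix them. Single-occurrence PCS counts do not change for an abnormality already seen on drug. What remains is:
- a first PCS or shifted value more than 5 days off drug, including one on a late ET panel;
- a consecutive pair that straddles day 5. Protocol 1.3 says rises appeared within the first 2 to 4 weeks, so a sustained rise would usually show as consecutive values on drug already;
- the PCS denominator, for a subject whose only post-baseline sample is late.

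**Step 3. Size.** One subject moves a percentage by 1/52 = 1.9 points per arm, or 1/26 = 3.8 points per arm within a stratum. The stratum figure applies only to single-occurrence PCS, the only PCS table repeated by stratum. The documents give no number affected. If it were 1, 2 or 3 subjects in an arm (assumption), the change would be 1.9, 3.8 or 5.8 points, or 3.8, 7.7 or 11.5 points if all were in one stratum.

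**Step 4. Which reading governs?** SAP 9.6 excludes late safety values outright and names one exception, adverse events. A further exception for PCS or shift counts would belong there, and none is given. The rule sits in section 9, the SAP's overall considerations, and agrees with SAP 9.2. In 12.2 both phrases follow summaries tied to a visit or to end of treatment, and they say that these counts pool over visits. The sections are compatible if 9.6 defines the eligible data and 12.2 defines the pooling.

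**Step 5. Is the governing rule sound?** Off-drug samples are taken mainly in subjects selected for an abnormal result, so pooling them with on-treatment counts would mix exposure states. The limit also protects the by-visit tables. A subject stopping on Day 40 would be rechecked on Days 40 + 11 = 51 to 40 + 17 = 57, inside the Week 8 window, and an off-drug value could be reported as Week 8.

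**Step 6. Does the limit hide recovery?** Not by itself. SAP 9.6 leaves the Follow-up Visit out of the windows. A completer with last dose on Days 82 to 85 would be rechecked between Day 82 + 11 = 93 and Day 85 + 17 = 102. That is 8 to 17 days from target, against 0 to 3 for the Week 12 sample, which would be chosen anyway. The off-drug values stay in the listings.

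**The case for a change.** The best argument for a change is that the broader reading of 12.2 is not careless. The limit appears under a heading about visit windows. SAP 12.2 describes the 2-week recheck and Follow-up tests shortly before defining these tables. Its shift text moves from end of treatment to the whole study within two sentences, which could be deliberate. One sentence would settle it, and one small table would show whether creatinine came back down.

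Part of this stands. There is no cross-reference, and the phrases are looser than they should be. But a heading does not narrow a rule that covers all safety parameters apart from adverse events, and describing when samples are collected does not say which table they enter.

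The recovery table is a separate request and weaker. Protocol 9.3.2 does not ask for it. It would hold few subjects, and their values are already listed. It could test the reversibility statement only in part: the recheck depends on a clinically significant creatinine result at Week 12 or ET, whereas PCS uses a fixed change from baseline. A subject who met the PCS limit earlier may have no off-drug sample.

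**Conclusion.** No change follows. This is a gap in cross-referencing that analysts fill sensibly by applying SAP 9.6 to every laboratory summary, including PCS numerators, denominators, consecutive pairs and study-wide shifts. The result is a coherent on-treatment description. Late values are in the listings. Late abnormalities that the investigator judges clinically significant are recorded as adverse events, and count as treatment-emergent if they start less than 30 days after last dose (SAP 12.1).

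The most that rests on the reading is 1.9 points per affected subject per arm, or 3.8 points per arm within a stratum for single-occurrence PCS, in tables with no formal testing (Protocol 9.3.2). The primary analysis, significance level and power are unaffected.

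This rests on two assumptions. First, all randomised subjects in an arm are assessed, so the denominators are 52 and 26. Second, the text not visible in the copy examined (anything in SAP 12.2 after Table 3, section 12.3, and the redacted 11.3) does not set a different rule. The number of affected subjects is unknown, but the choice of SAP 9.6 does not depend on it.
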